12.5.4 Pooling Analysis

The clinical study will be conducted under a common protocol for each investigational site with the intention of pooling the data for analysis. Every effort will be made to promote consistency in study execution at each study site. The study is intended to be conducted in a manner such that a minimum of 15 subjects will be randomized and included in the ITT population (i.e., approximately at least 10 subjects in the IDP-124 Lotion arm and at least 5 subjects in the Vehicle Lotion arm) for any investigational site. In the event that there are too few subjects in a treatment arm for an investigator, then the investigator's data will be combined to achieve the desired sample size minimum per treatment arm. The combining of investigator data will be accomplished, within geographic region, by taking the investigator with the smallest enrollment and combining it with the investigator with the largest, restricted to investigational sites that did not meet minimum enrollment. If there is a further need to combine data, then the data of the investigator with the second smallest enrollment will be combined with the investigator's data which had the second largest enrollment, and so on. This process will continue for all investigators who did not have a minimum of 15 subjects enrolled. The process of combining investigator data that have insufficient subjects per treatment arm will result in redefining the groups of investigators for the purposes of

statistical analyses. These combined groups will be referred to as "analysis centers" in the statistical analyses.

The consistency of treatment response will be investigated across the analysis centers subsequent to combining the data as described above. Statistical tests will be conducted to identify if there are extreme analysis centers that could affect the interpretation of common statistical and clinical conclusions. For the purpose of testing consistency of treatment response, the primary efficacy variable will be considered. The percent of subjects with treatment success at Week 6 will be analyzed with a logistic regression with factors of treatment group, analysis center, and the interaction term of treatment group by analysis center. Further examination will follow if the analysis results in a significant interaction term.

In the event that the logistic regression interaction p-value is less than or equal to 0.10, a sensitivity analysis that excludes analysis centers with the extreme efficacy result will be performed to determine the robustness of the treatment effect. On the other hand, if the analysis results in an interaction terms with p-value greater than 0.10, then the conclusions from the pooled data will be considered to be free of the impact of extreme analysis centers.

The first step in conducting a sensitivity analysis is to identify the extreme analysis center or centers that contribute to the statistical significance of the interaction term of the logistic regression. The process involves submitting subsets of analysis centers to the logistic regression and observing the interaction p-value for the subset. Subsets resulting in interaction p-values greater than 0.10 are considered homogeneous.

The search for an extreme analysis center begins by analyzing all subsets that can be created by excluding 1 analysis center. If 1 or more of the subsets result in an interaction p-value greater than or equal to 0.10, then the analysis center excluded from the subset with the largest interaction p-value is deemed the extreme analysis center.

If all subset interaction p-values are less than or equal to 0.10, then the process will analyze the interaction for all subsets that can be created by excluding 2 analysis centers. If 1 or more of these subsets generate interaction p-values larger than 0.10, then the analysis centers excluded from the subset with the largest interaction p-value are deemed the extreme analysis centers.

Thus, the process of identifying the extreme analysis centers will continue in a stepwise manner by first excluding 1, then 2, then 3, etc, analysis centers until the logistic regression interaction p-value exceeds 0.10.

Once the extreme analysis center or centers have been identified, then the treatment p-values of the remaining analysis centers will be computed. Inferences will be drawn from the treatment p-value, as well as any pertinent observations regarding the extreme analysis center

or centers. Additionally, it is noted that this process excludes subjects from the analysis in a nonrandom manner and has an unpredictable impact on the power of the treatment effect test.

In the event that the treatment effect of the remaining subset is not statistically significant, due consideration of the post hoc aspects of the process will be given when the results are interpreted. Conclusions will be presented by the sponsor as appropriate to the findings of the sensitivity analysis.

Prior to investigating the treatment effect within the analysis centers, the magnitude of the site main effect will be investigated to determine if the main site-to-site variability is such that it could mask the analysis center effects. Thus, prior to pooling, the percent of subjects with treatment success at Week 6 will be analyzed with a logistic regression with factors of treatment group, site, and the interaction term of treatment group by site. If the analysis is not computationally feasible due to some sites having very few subjects enrolled, the low enrolling sites will be excluded from the analysis.

12.5.5 Sensitivity Efficacy Analyses

12.5.5.1 Analyses Using Last Observation Carried Forward

In the first set of sensitivity analyses, missing IGA values will be imputed using LOCF. Treatment success at Week 6 will be analyzed as it was in the primary analyses. Comparisons will be performed on imputed data using CMH tests stratified by analysis center.

12.5.5.2 Repeated Measures Analysis on Observed Data

As a second sensitivity analysis, treatment success at Week 6 will be analyzed with a repeated measures logistic regression model (generalized estimating equations), with treatment success as the dependent variable and treatment, analysis center and visit (Weeks 1, 2, , 4 and 6) as independent factors.

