12.5.1 Primary Efficacy

The primary efficacy endpoint will be used to compare twice daily application of IDP-124 Lotion and Vehicle Lotion.

The percentage of subjects with treatment success at Week 6 will be analyzed using CMH test stratified by analysis center.

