12.5.2 Secondary Efficacy

The secondary efficacy endpoints will be:

- Dichotomized IGA score at Week 4 where treatment success is defined as achieving clear to almost clear (i.e., a score of 0 or 1) and at least a 2-grade improvement in the IGA. These data will be analyzed using the CMH test stratified by analysis center.
- The percentage of subjects with EASI 75 (at least a 75% reduction) at Week 6 where the EASI score is defined as a composite score based on the evaluated severity of 4 key signs of AD (i.e., erythema, infiltration/papulation, excoriation, and lichenification), and the extent of disease in each of the 4 body regions (i.e., head/neck, trunk, upper limbs, and lower limbs) will be analyzed using the CMH test stratified by analysis center.
- The percentage of subjects with EASI 75 (at least 75% reduction) at Week 4 will be analyzed using the CMH test stratified by analysis center.
- Dichotomized IGA score at Week 10 where treatment success is defined as achieving clear to almost clear (i.e., score of 0 or 1) and at least a 2-grade improvement in the IGA from Baseline. These data will be analyzed using the CMH test stratified by analysis center.
- The percentage of subjects with EASI 75 (at least 75% reduction) at Week 10 will be analyzed using the CMH test stratified by analysis center.
- Percentage of subjects with score of "None" or "Mild" and at least a one-grade improvement from Baseline in the severity of pruritus at Week 2
- Percentage of subjects with score of "None" or "Mild" and at least a one-grade improvement from Baseline in the severity of pruritus at Week 1Dichotomized IGA score at Week 2 where treatment success is defined as achieving clear to almost clear (i.e., score of 0 or 1) and at least a 2-grade improvement in the IGA from Baseline. These data will be analyzed using the CMH test stratified by analysis center.

Evaluation of the secondary efficacy variables will use a gated sequential procedure starting with the comparisons of the first bulleted item and proceeding onto the next item. The process will terminate if a nonstatistically significant value is observed.

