12.5.5.3 Tipping Point Analysis

A tipping point analysis of the primary endpoint will be performed as a sensitivity analysis for the handling of missing data.

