12.8.2 Sample Size Determination

The following power calculations were computed using the IGA efficacy results from the Pimecrolimus Lotion, 1% (Elidel) NDA 21-302. Considerations were given the change in expected entry level severity of the current study. Nquery Advisor Version 7.0 with the Fisher's exact test option was used to calculate the power using a 2-sided test with an alpha of 0.05. The following table presents the efficacy estimates used in this power calculation.

Percent Dichotomized IGA Success* for Treatment Groups

	Pimecrolimus Lotion, 1%	Vehicle
Percent	23.6%	6.3%
Success		

* Success was defined as at least a 2-grade improvement from Baseline in the IGA score and an IGA score equating to "Clear" or "Almost Clear".

Overall, 232 IDP-124 Lotion treated subjects and 116 vehicle lotion treated subjects will have greater than 95% power to detect a statistically significant outcome for a 2-sided test with an alpha level of 0.05.

It was noted that the estimates extracted from the above studies are based on the LOCF method of handling missing values while the proposed Phase 3 analysis will account for missing values using multiple imputations. The power stated above sufficiently exceeds 95% which will compensate for the difference in handling of missing data.

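### The GEE sensitivity analysis is labelled a Week 6 analysis, but the factors listed give a single odds ratio shared by Weeks 1, 2, 4 and 6

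*Combined protocol and SAP*

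**What the plan says.** The primary analysis (12.5.1) is for Week 6: "The percentage of subjects with treatment success at Week 6 will be analyzed using CMH test stratified by analysis center". Three sensitivity analyses follow in 12.5.5.

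- LOCF (12.5.5.1) keeps that target: "Treatment success at Week 6 will be analyzed as it was in the primary analyses".
- Repeated measures (12.5.5.2) names the same target: "treatment success at Week 6 will be analyzed with a repeated measures logistic regression model (generalized estimating equations". It then gives the model as "treatment success as the dependent variable and treatment, analysis center and visit", the visits being Weeks 1, 2, 4 and 6. It mentions no treatment-by-visit interaction, Week 6 contrast or working correlation.
- Tipping point (12.5.5.3) gives no model but names the target: "A tipping point analysis of the primary endpoint will be performed as a sensitivity analysis for the handling of missing data".

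Section 12.5.2 makes the Week 4 outcome ("Dichotomized IGA score at Week 4 where treatment success is defined as achieving clear to almost clear") and the Week 2 outcome ("IGA score at Week 2 where treatment success is defined as achieving clear to almost clear") separate secondary endpoints. Sections 12 and 12.8 leave the full description of all analyses to a separate SAP. None of the text supplied specifies this model further.

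**The concern.** The named target and the stated model disagree. A logistic model with main effects for treatment, center and visit has one treatment coefficient, which applies to all four visits. Nothing in it is a Week 6 treatment effect.

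An interaction cannot simply be read in. Section 12.5.4 names interaction terms explicitly where they are wanted (treatment by analysis center, treatment by site).

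A sensitivity analysis of the primary endpoint should show whether the Week 6 conclusion survives a different treatment of missing data. Here a departure from the primary could arise only because the effect grows or fades between Week 1 and Week 6, and a reader could not tell the two causes apart. The reported odds ratio would also blend Week 6 with outcomes that the plan tests as endpoints of their own.

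**Working it through.** **1. Inputs and the plan's own figure.** Under "Percent Dichotomized IGA Success* for Treatment Groups", Section 12.8.2 gives 23.6% active and 6.3% vehicle, with 232 and 116 subjects, Fisher's exact test and two-sided alpha 0.05. Exact enumeration gives power of 99.3%, which agrees with the stated figure of more than 95%. That figure is not in dispute. The table names no visit; its rates are taken here as Week 6.

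**2. Week 6 odds ratio.** (0.236/0.764) / (0.063/0.937) = 0.3089/0.0672 = 4.59.

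**3. What the stated model estimates.** logit P(success) = intercept + β·treatment + center + visit. β carries no visit index, so exp(β) is one ratio for all visits. Under independence its estimating equation is Σ over subjects and visits of treatment × (observed − fitted) = 0, which pools the four visits.

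**4. Large-sample value of exp(β).** I solved the estimating equations for treatment + visit with 2:1 allocation, complete data and no center effect. Rates at Weeks 1, 2 and 4 are assumptions. Vehicle is 2/3.5/5.5%, except in the early-onset row, where it is 1/2.5/4.5%. Week 6 is 23.6% vs 6.3% throughout.

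| Scenario | Active, Weeks 1/2/4 | Odds ratios, Weeks 1/2/4/6 | Independence | Exchangeable 0.25 | Exchangeable 0.5 |
|---|---|---|---|---|---|
| A constant | 8.6/14.3/21.1% | 4.59 at each | 4.59 | 4.59 | 4.59 |
| M mild growth | 4.9/9.8/18.9% | 2.5/3.0/4.0/4.59 | 3.81 | 4.08 | 4.6 |
| B delayed onset | 3/7/14% | 1.52/2.08/2.80/4.59 | 3.10 | 3.56 | 4.48 |
| C very late onset | 2/4/9% | 1.00/1.15/1.70/4.59 | 2.46 | 3.16 | 4.77 |
| Early onset | 8/15/21% | 8.61/6.88/5.64/4.59 | 5.63 | 5.38 | 5.01 |

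A constant ratio is sufficient for agreement but not necessary. With active 5/9/28.2% at Weeks 1, 2 and 4 and the 2/3.5/5.5% vehicle rates, the ratio varies by visit, yet the common value is again about 4.6 under independence.

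**5. Effect in trials of this size.** Simulation of 4000 trials per scenario with 232/116 subjects. Assumptions: Gaussian copula with AR(1) correlation 0.7 per visit step, 12 equal analysis centers as factors and no true center effect. Robust standard errors; Monte Carlo error at most 0.7 points. Entries are independence / exchangeable, complete data.

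| Scenario | Median common odds ratio | GEE power | Primary significant, GEE not |
|---|---|---|---|
| A | 4.82 / 4.83 | 100 / 100% | 0.0 / 0.1% |
| M | 3.94 / 4.22 | 99.6 / 99.7% | 0.4 / 0.2% |
| B | 3.18 / 3.64 | 96.1 / 98.2% | 3.5 / 1.3% |
| C | 2.55 / 3.17 | 80.3 / 92.4% | 19.0 / 6.9% |

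The Week 6 CMH test had power of 99.3–99.5%. A Week 6 contrast from a model with treatment-by-visit had a median odds ratio of 4.8–4.9 in all four scenarios, and at most 0.1% of trials had a significant primary with a non-significant contrast. The medians sit slightly above the large-sample values (4.8 against 4.59 in A, small-sample bias), so 4.8–4.9 is the comparator.

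With 12–13% missing at Week 6 (assumed: dropout 4% active and 6% vehicle before Weeks 2, 4 and 6 among subjects not in success), the proportion with primary significant but GEE not is 6.1/2.6% in B and 28.8/11.4% in C. With the Week 6 contrast it is about 1%. The complete-data CMH stands in here for the multiply imputed primary.

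**The case against.** The strongest reply concerns consequence. This is the second of three sensitivity analyses and no decision rule uses it. LOCF and the tipping point still address the primary endpoint. With a constant odds ratio there is no bias, and with mild change the significance verdict moves in at most 0.4% of trials. All of that stands and limits the weight of the point.

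Second, every rate before Week 6 is assumed, and so is the within-subject correlation. Scenario C, in which active success jumps from 9% at Week 4 to 23.6% at Week 6, has no support in the documents and should carry little weight. The simulations cover only a constant or growing effect; early onset is no less plausible and pushes the ratio up. The exchangeable values also vary widely: B runs from 3.56 at correlation 0.25 to 4.48 at 0.5. These are fair limits on the numbers. They do not touch the structural point, and the spread itself shows that the unstated working correlation matters for the common ratio.

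Third, the separate SAP may already contain the contrast. That cannot be excluded, but 12.5.5.2 as written does not.

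Finally, a treatment-by-visit model under independence comes close to an observed-case Week 6 logistic analysis and gives up the precision of pooling visits. That is true. Relabelling the estimate as an average over visits would also remove the contradiction.

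**Conclusion.** The concern holds. As written, 12.5.5.2 promises a Week 6 result from a model that returns one odds ratio common to Weeks 1, 2, 4 and 6. This follows from the factor list alone and needs no assumption about rates.

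The size of the discrepancy does need assumptions. Against a Week 6 ratio of 4.59, the scenarios give common ratios from 2.46 to 5.63, or 3.10 to 5.63 if the very late onset case is set aside. In most plausible settings the reported effect size is off more than the significance verdict. The primary CMH test and its power are unaffected. The text should be corrected before unblinding, because choosing between a common ratio and a Week 6 contrast afterwards would be data-driven.

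**What to change.** In 12.5.5.2, and in the separate SAP unless it already does so:

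- Add treatment-by-visit, with visit categorical (Weeks 1, 2, 4, 6), and report the Week 6 treatment odds ratio with its 95% CI as the sensitivity result.
- Prespecify one working correlation, for example exchangeable, with robust standard errors. For the contrast the choice hardly matters: in B the median is 4.79 under both structures, and 4.82 vs 4.91 (independence vs exchangeable) with missing data.
- State a fallback for sparse cells: drop Week 1 if an arm has no success there or the model does not converge. If it still cannot be fitted, use the observed-case Week 6 CMH test stratified by analysis center.

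If an average over visits is what is intended, say so and remove the Week 6 label.

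The cost is one model term, one contrast and two sentences, with no new data. If the odds ratio really is constant, the contrast is less precise: the median standard error of the log odds ratio in A is 0.42 against 0.33, and 0.42/0.33 = 1.27, so the interval is about 27% wider on the log scale. The fallback will sometimes be needed. With vehicle Week 1 success of 1% or 2% (assumed), the chance of none among 116 is 0.99^116 = 31% or 0.98^116 = 10%. In the simulations it was used in 10–13% of trials, and 1–2% reached the CMH step.

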12.5.5.3 Tipping Point Analysis

A tipping point analysis of the primary endpoint will be performed as a sensitivity analysis for the handling of missing data.

12.5.6 Subgroup Analyses

Subgroup analyses will be conducted for the ITT population for the following subgroups: Baseline IGA, sex, age, ethnicity, race, and geographic region. Subgroup analyses will be conducted on the primary efficacy endpoint and will contain only descriptive statistics.

12.6 Safety

12.6.1 Adverse Events

The primary analysis of safety will be conducted at Week 6. There will be a separate tabulation of the AEs that start in the period post Week 6, to Week 10 visit. All AEs occurring during the study will be recorded and classified using terminology from the Medical Dictionary for Regulatory Activities (MedDRA). All reported treatment-emergent adverse events (TEAEs), defined as any AE with an onset on or after the date of first study drug application, will be summarized by treatment group and will provide the number of subjects reporting TEAEs, system organ class, preferred term, severity, and relationship to study drug. When summarizing TEAEs by severity or relationship to study drug, each subject will be counted only once within a system organ class or a preferred term using the event with the greatest severity or causality, respectively, within each category. All reported SAEs will be summarized by the number of subjects reporting the event, system organ class, preferred term, severity, and relationship to study drug.

All information pertaining to AEs noted during the study will be listed by treatment group and subject and will include a verbatim description of the event as reported by the investigator, as well as the preferred term, system organ class, start date, stop date (if stopped), seriousness, severity, action taken regarding the study drug, corrective treatment, outcome, and relationship to the study drug. In addition, a listing of subjects who prematurely discontinue from the study due to AEs will be provided as well as a listing of subjects who reported an SAE.

